### **1.5 Dose Rationale and Risk/Benefits**

As previously stated Drs. [name] and [name] are currently conducting a 12-month RCT (MHR01087619) designed to identify predictors of mood and cardiovascular benefit of transdermal estradiol in perimenopausal women. This study will enroll perimenopausal women to undergo estradiol supplementation using their existing infrastructure. Many studies have identified perimenopausal women as being at high risk for mood disorders, especially during the late menopause transition, but only a few studies have systematically assessed this biological vulnerability. The benefits of this study are three-fold: 1) increased knowledge of the neuroendocrine mechanisms underlying both the triggering of and susceptibility to depression in women, 2) improved identification of perimenopausal women for whom hormone replacement therapy is likely to have beneficial neuroregulatory effects, and 3) increased information regarding novel targets for pharmacologic intervention. While there are scientific benefits to this study, the benefit to patients will be minimal. Estradiol administration may reduce depressive symptoms in some of the participants, and this information may be helpful to women as they plan their future health care in relation to menopause symptom management.

## **2 Study Objectives**

The long-term research objectives are to 1) advance our understanding of the effects of ovarian hormones on the female brain and how these effects contribute to the triggering of and susceptibility to mood disorders; and 2) to identify neural and endocrine markers of depression risk, thereby improving our ability to prevent affective illness in women.

The central hypothesis is that the neural reward system is hypoactive in perimenopausal MDD, and the antidepressant effects of a three-week transdermal estradiol intervention will be mediated by increased activity in the neural reward system, assessed using fMRI. We will test our hypothesis by executing the following aims:

**Aim 1: To measure the frontostriatal response to reward in perimenopausal MDD and test the effects of estradiol on neural activation in perimenopausal women.** We will use fMRI at baseline and following estradiol treatment in women with and without MDD to probe frontostriatal reward circuitry. Implementation of this protocol will provide hands-on training in fMRI research, the experimental manipulation of sex steroids in humans, and the interpretation of fMRI results based on a pharmacologic manipulation.

*H1a:* We expect women with perimenopausal MDD to show reduced frontostriatal reactivity to reward at baseline compared with perimenopausal women without MDD. Specific regions of interest include the nucleus accumbens, caudate, and putamen.

*H1b:* We also expect that estradiol administration will be associated with greater increases in frontostriatal responsivity to reward in those with MDD compared with those without MDD.

**Aim 2: To quantify motivated behavior at baseline and following estradiol administration in perimenopausal women with and without MDD.** Motivated behavior will be operationally defined as the response latency to reward versus non-reward during the fMRI reward task. Pursuit of this aim will provide training in behavioral markers of psychopathology in the context of fMRI.

*H2a:* Women with perimenopausal MDD will show greater response latencies during reward trials but not non-reward trials compared with those without MDD.

*H2b:* We also expect that response latency to reward will be attenuated with estradiol administration in women with MDD.

**Aim 3: To measure dysphoria at baseline and following estradiol administration.** Dysphoria will be assessed at baseline and following estradiol administration. Training associated with this aim will include assessing associations between neural activity and psychological symptoms.

*H3a:* Women with perimenopausal MDD will report a significant reduction in depressive symptoms following estradiol administration, and the degree of symptom improvement will be associated with the change in frontostriatal responsivity to reward.

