Statistical Methodology	
This study has one between-subjects factor (group: MDD versus control) crossed with one within-subjects factor (time: baseline versus estradiol treatment) with the outcome (percent signal changed) assessed in response to the MID task in the structurally defined frontostriatal ROIs, including the nucleus accumbens, caudate, thalamus, frontopolar cortex, and dorsolateral prefrontal cortex. Thus, for a task/ROI combination, there is a 2-by-2 repeated measures design. We will analyze this design using an ROI analysis and mixed models with an unstructured covariance structure. To test whether perimenopausal women with MDD show reduced frontostriatal activity and motivated behavior in response to reward at baseline, we will examine group differences in BOLD signal and response latency at baseline. To measure the psychological correlates of the frontostriatal response to reward, we will examine correlations between the change in frontostriatal ROI activation and change in depressive symptoms in the MDD group between baseline and post-treatment; also within the MDD group, we will examine the correlation between frontostriatal ROI activity at baseline and the change in depressive symptoms between baseline and post-treatment. Finally, to examine whether estradiol treatment has greater effects on women with MDD than those without, we will assess whether the groups differ with respect to the change from baseline to post-treatment in percent activation in frontostriatal ROIs and response latency.
															

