### FMRI Tasks

The following task will be included in each of the two fMRI sessions:

The Monetary Incentive Delay (MID) Task engages the reward circuitry during monetary incentive anticipation and outcomes. Each of two MID runs consists of 90 6-second trials during which subjects are presented with one of nine cue shapes, a fixation crosshair (for a variable duration), the target, and performance (win/loss/neutral) feedback. The cue indicates whether it is an incentive (gain, loss) or non-incentive trial. During incentive trials, participants can either gain or lose money by pressing a button during target presentation. Task difficulty is based on participant reaction times. This task elicits reliable frontostriatal dysregulation in people with remitted MDD. Resting state scans will also be conducted at the beginning and end of each session. The Hariri Emotional Faces Task is an emotional face-matching task that engages neuronal regions implicated in emotional processing, including the amygdala and dorsomedial PFC. This block design paradigm consists of 4 blocks of a perceptual face-processing task interleaved with 5 blocks of a sensorimotor control task. Participants are presented with a target stimulus and asked to select one of 2 images, presented on the low half of the screen, which match the target. Each face-processing block consists of fear and anger sub-blocks. During the sensorimotor control blocks, subjects view a trio of simple geometric shapes. Notably, this task elicited differences in amygdala activation between women with PPD and euthymic postpartum women in a previous study of PPD.

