### **3.2 Primary Study Endpoints**

1. Frontostriatal reactivity to reward during the MID fMRI task
2. Response latency to reward versus non-reward during the MID fMRI task
3. Depressive symptoms

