### 7.2 Statistical Methods

This study has one between-subjects factor (group: MDD versus control) crossed with one within-subjects factor (time: baseline versus estradiol treatment) with the outcome (percent signal changed) assessed in response to the MID task in the structurally defined frontostriatal ROIs, including the nucleus accumbens, caudate, thalamus, frontopolar cortex, and dorsolateral prefrontal cortex. Thus, for a task/ROI combination, there is a 2-by-2 repeated measures design. We will analyze this design using an ROI analysis and mixed models with an unstructured covariance structure. To test whether perimenopausal women with MDD show reduced frontostriatal activity (H1) and motivated behavior (H2) in response to reward at baseline, we will examine group differences in BOLD signal and response latency at baseline. To measure the psychological correlates of the frontostriatal response to reward, we will examine change in depressive symptoms between baseline and post-treatment in MDD relative to controls (H3).

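### The latency analysis never names the reward-versus-non-reward contrast that primary endpoint 2 describes, so general slowing or speeding could be reported as a motivational effect

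*Combined protocol and SAP*

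**What the plan says.** Section 2 (Aim 2) and the Study Summary define the construct: "Motivated behavior will be operationally defined as the response latency to reward versus non-reward during the fMRI reward task". Section 3.2 lists it as one of three primary endpoints: "Response latency to reward versus non-reward during the MID fMRI task". None of these places gives a formula, so the measure could be a difference, a ratio or two separate latencies.

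The hypotheses are worded differently from the endpoint. H2a expects women with MDD to show "greater response latencies during reward trials but not non-reward trials" compared with controls, which is a difference on one trial type and none on the other. H2b expects that "response latency to reward will be attenuated with estradiol administration in women with MDD", with no non-reward comparator.

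The analysis text is shorter still. For H2, section 7.2 says "we will examine group differences in BOLD signal and response latency at baseline". The Study Summary adds a comparison of whether "the groups differ with respect to the change from baseline to post-treatment in percent activation in frontostriatal ROIs and response latency". Neither place mentions a trial-type factor, a contrast score, or what evidence would support the non-reward half of H2a.

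The data for the contrast are collected. On the task, section 3.1 (FMRI Tasks) says: "The cue indicates whether it is an incentive (gain, loss) or non-incentive trial".

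**The concern.** Raw latency mixes motivation with general speed. A claim that slowing is specific to reward is a claim about the difference between two trial types, that is, a group-by-trial-type interaction. A significant group difference on reward trials beside a non-significant one on non-reward trials does not test that difference. At 20 per group, a non-significant non-reward test is also weak evidence that no difference exists.

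An analyst following the plan could use reward-trial latency, latency pooled over trials, two separate tests, or a difference score. Only the last isolates what Aim 2 calls motivated behavior. Under the others, women who are simply slower on every trial could be reported as having a motivational deficit on a primary endpoint.

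H2b has a parallel problem. It is a statement about women with MDD over two sessions, there is no placebo arm, and section 1.1 acknowledges that a placebo condition would have controlled for variance from repeated fMRI. A within-MDD fall in reward latency could be familiarity with the task as easily as estradiol.

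**Working it through.** **The plan's own figure.** Section 7.1 states 80% power for an effect size of 0.9 with 20 per group, for a two-group comparison of change scores. Alpha is not stated; I assume 0.05 two-sided. The normal approximation gives 81.2%, and the noncentral t with 38 df gives 79.2%. The figure reproduces. It was not derived for the latency contrast.

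**Inputs.** From the plan: 20 per group. Assumed, because the documents give no values: the size *d* of general slowing in MDD (0.5 to 0.9), the correlation rho between a woman's reward and non-reward latency (0.6 to 0.9), and equal SDs on the two trial types. The upper value 0.9 is borrowed from the plan's power target and is not an estimate of slowing.

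**1. Reward-only test when both trial types are slowed equally.** The noncentrality is d × √(20/2) and the critical t is 2.024.
- d = 0.5: noncentrality 1.58, significant 34% of the time.
- d = 0.7: noncentrality 2.21, 58%.
- d = 0.9: noncentrality 2.85, 79%.

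There is no reward-specific effect in any of these cases.

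**2. Two separate tests under the same equal slowing.** I simulated 40,000 studies per setting. The table gives the share showing significant slowing on reward and a non-significant result on non-reward.

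| rho | d = 0.5 | d = 0.7 | d = 0.9 |
|---|---|---|---|
| 0.6 | 13% | 14% | 11% |
| 0.7 | 12% | 12% | 9% |
| 0.8 | 9% | 10% | 7% |
| 0.9 | 7% | 7% | 5% |

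**3. Group-by-trial-type test.** This is the group comparison of non-reward minus reward latency. In the same simulations it rejects 4.9% to 5.1% of the time. About half of those rejections (2.5%) are in the direction of H2a, which is the like-for-like figure against step 2.

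**4. Power of the contrast for a truly reward-specific slowing of d = 0.9.** The difference score has variance 2(1 − rho) times that of a single condition, so its standardised effect is 0.9 / √(2(1 − rho)).
- rho = 0.3: 0.9/√1.4 = 0.76, power 65% (28 per group needed for 80%).
- rho = 0.5: 0.9/√1.0 = 0.90, power 79%, the same as a reward-only test.
- rho = 0.7: 0.9/√0.6 = 1.16, power 95%.
- rho = 0.8: 0.9/√0.4 = 1.42, power 99%.

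**5. H2b, by reading.** Let general speeding at session 2 be *s*, equal on both trial types.
- A within-MDD test of reward latency estimates the estradiol effect plus *s*.
- The Study Summary's group comparison of change removes *s* if it is the same in both groups, but not if it differs in MDD.
- The change in non-reward minus reward latency removes *s* in either case.

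**The case against.** The strongest reply is that the contrast is already the defined outcome. Aim 2 and endpoint 2 both say reward versus non-reward. If response latency in section 7.2 is shorthand for that measure, and the measure is a difference score, then the group comparison in 7.2 is already the interaction test and only a wording gap remains. That reading is available, so a reader should not infer that the plan rules out the right test. But no section gives the formula, H2a is framed as two simple effects, and H2b drops the non-reward comparator. The plan therefore permits the wrong analyses as readily as the right one.

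Four stronger readings are tempting and are not supported.
- *Equal slowing on both trial types would confirm H2a.* By its own words H2a fails if slowing is also seen on non-reward trials. The 34% to 79% therefore applies only if latency is analysed on reward trials alone; with both trial types tested separately, the relevant rate is 5% to 14%.
- *Any practice effect would pass as H2b.* The Study Summary's between-group comparison of change cancels speeding shared by both groups. The exposure is a within-MDD test, or speeding that differs by group.
- *Section 7.2 commits latency to a group-by-time model.* That sentence is written for percent signal change. For latency, 7.2 gives only the baseline comparison.
- *The contrast always gains power.* It does so only when rho exceeds about 0.5.

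It is also fair to say that section 1.1 presents the study as pilot data for a larger trial. That limits the consequences but does not change which test answers Aim 2.

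**Conclusion.** The concern holds as a failure to tie a primary endpoint to a named test. Under equal slowing in MDD with 20 per group, a reward-only analysis is significant about 34% to 79% of the time, and two separate tests give the false H2a pattern about 5% to 14% of the time. The group-by-trial-type test stays near 5% two-sided. These rates rest on assumed slowing (d 0.5 to 0.9), assumed rho (0.6 to 0.9), equal SDs and two-sided 0.05; they show what the wording allows, not what will happen. For H2b, reward latency within MDD cannot separate estradiol from general speeding, and the between-group comparison of change only partly repairs this. The stated sample size is not in error.

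**What to change.** In section 7.2:
- Define the latency outcome as each woman's non-reward minus reward (gain) latency, per session, and say whether loss trials are excluded from non-reward.
- Test H2a as the group difference in that score at baseline, which is the group-by-trial-type interaction. Reward-specific slowing in MDD makes the score smaller.
- Test H2b as the change in that score within MDD, and compare the change between groups.
- Report reward and non-reward latencies separately beside the contrast. A smaller score can also arise if women with MDD are faster on non-reward trials, so the direction must be visible.
- State that a non-significant non-reward result will not be read as absence of a difference.

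Reword H2a and H2b to match, and carry the same text into the Study Summary.

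The cost is wording: both trial types are already in the task, and no visits or participants are added. The downside is power if rho is low, about 65% at rho 0.3 for a reward-specific d of 0.9, against 79% for a reward-only test.

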### 3 Study Design

#### 3.1 General Design

Overview. This is an observational, case-control, single-center study using estradiol and progesterone to examine the role of frontostriatal hypoactivity in the pathophysiology of perimenopausal MDD (by assessing baseline differences between perimenopausal MDD and controls.) It will also allow us to measure frontostriatal responses to estradiol treatment in both perimenopausal MDD and control women. This study will include 6 study visits that will take place over the course of approximately 6 weeks. Participants will receive transdermal estradiol for 3 weeks and FMRI sessions will occur at baseline and at the end of the third week of estradiol administration. The procedures that will take place are outlined in **Table 1** and detailed below.

**Table 1. Study Procedures and Timeline**

Study visit	1	2	3	4	5	6
Consent	x					
OBGYN Exam		x				
fMRI			x			x
PRT			x			x
Venipuncture		x	x	x	x	x
SCID	x					
SNAP	x					

HAM-D	x		x	x	x	x
IDAS	x		x	x	x	x
PANAS	x		x	x	x	x
MASQ	x		x	x	x	x
GCS	x		x	x	x	x
PSQI			x			x
Estradiol Rx provided			x	x	x	x
Progesterone Rx provided						x
Payment	\$100	\$30	\$150	\$35	\$35	\$150

**Participants.** Participants will include healthy, unmedicated perimenopausal women ages 44-55 either with ( $n=20$ ) or without ( $n=20$ ) current major depression.

**Hormone Administration.**

In the OBGYN visit, women will have a basic lab panel and serum pregnancy test performed, and FSH and LH will be assayed. Prior to estradiol administration women will receive a pelvic exam, breast exam and Papanicolaou test. Participants who can provide record of a pelvic exam within the past year and a normal pap results within the past 3 years will be permitted to decline the GYN exam and. Women will be seen in the clinic each week during estradiol administration to assess blood levels of estradiol and mood symptoms. Women will receive an additional week of combined estradiol and micronized progesterone (200 mg/day) at the end of the study to precipitate menstruation. Blood will be batched until the end of data collection, at which point estradiol will be assayed.

**Clinical Assessments**

The Structured Clinical Interview for DSM-IV-TR Axis-I Disorders (SCID) and the Schedule for The SCID1 will be administered at baseline to determine study eligibility. The following standard measures will be administered at baseline, both fMRI sessions, and weekly clinic visits:

- The Positive and Negative Affect Schedule is a 20-item questionnaire that measures both positive affect (PA) and negative affect (NA) and is sensitive to subtle changes in affect over time.
- The Hamilton Rating Scale for Depression (HRSD) is a 21-item researcher-rated standardized scale that assesses depressive symptoms and is widely used as a measure of symptom change over time.
- The Inventory of Depression and Anxiety Symptoms (IDAS) is a 64-item self-report questionnaire that comprehensively assesses anxiety and depression symptoms on 10 subscales. The IDAS has excellent psychometric properties and has been validated for assessing reproductive mood disorders.
- The Mood and Anxiety Symptom Questionnaire - Anhedonic Depression Subscale (MASQ-AD) is a 22-item scale that assesses anhedonia (i.e., loss of interest and low positive affect). MASQ-AD scores have been associated with blunted striatal response to reward in previous studies of patients with depression.
- The Greene Climacteric Scale (GCS) is a 21-item scale that is the gold-standard measure of four domains of climacteric symptoms: vasomotor, somatic, anxiety, and depression.
- The Pittsburgh Sleep Quality Index (PSQI) is a 9-item questionnaire that measures the quality and sleep patterns in older adults. \*This measure will only be administered at the two fMRI sessions.

While the SCID and HAM-D are researcher administered, the other measures will be collected through self-report questionnaires using *Qualtrics* or paper and pencil questionnaires.

Despite the use of exclusion criteria designed to reduce risk to participants, depressive symptoms are monitored closely. Any subject who develops severe depressive symptoms (e.g., suicidal ideation) will be discontinued from the study and offered treatment paid for by the study. If inpatient hospitalization becomes

necessary as a result of the study, UNC Health Care will cover the cost. The following language has been added to the study consent form to reflect this policy:

### FMRI Tasks

The following task will be included in each of the two fMRI sessions:

The Monetary Incentive Delay (MID) Task engages the reward circuitry during monetary incentive anticipation and outcomes. Each of two MID runs consists of 90 6-second trials during which subjects are presented with one of nine cue shapes, a fixation crosshair (for a variable duration), the target, and performance (win/loss/neutral) feedback. The cue indicates whether it is an incentive (gain, loss) or non-incentive trial. During incentive trials, participants can either gain or lose money by pressing a button during target presentation. Task difficulty is based on participant reaction times. This task elicits reliable frontostriatal dysregulation in people with remitted MDD. Resting state scans will also be conducted at the beginning and end of each session. The Hariri Emotional Faces Task is an emotional face-matching task that engages neuronal regions implicated in emotional processing, including the amygdala and dorsomedial PFC. This block design paradigm consists of 4 blocks of a perceptual face-processing task interleaved with 5 blocks of a sensorimotor control task. Participants are presented with a target stimulus and asked to select one of 2 images, presented on the low half of the screen, which match the target. Each face-processing block consists of fear and anger sub-blocks. During the sensorimotor control blocks, subjects view a trio of simple geometric shapes. Notably, this task elicited differences in amygdala activation between women with PPD and euthymic postpartum women in a previous study of PPD.

### FMRI Data Acquisition and Image Processing

Scanning is performed using a Siemens Magnetom 3T TIM Trio scanner. High-resolution, T1-weighted anatomical images will be acquired using an MPRAGE sequence. Whole-brain functional images will be acquired using a single-shot, gradient recalled echoplanar pulse sequence sensitive to blood-oxygen-level-dependent (BOLD) contrast. Each of 2 runs will consist of the acquisition of 195 successive brain volumes. FMRI image preprocessing, processing, and analysis will be conducted using FSL and custom MATLAB scripts. FMRI analyses will include an event-related BOLD response analysis within *a priori* structurally defined frontostriatal regions of interest (ROIs). Contrasts of interest will include win versus non-win outcomes, although the anticipation of wins will also be explored.

